Hypothesis 1: We hypothesize that there will be an incremental benefit to augmenting working memory focused cognitive remediation with tDCS. Specifically, we predict that repeated administration of tDCS will produce 1) greater gains on novel versions of training tasks, 2) greater generalization of performance gains to conceptually similar (near transfer) and related cognitive processes (far transfer), 3) greater change in functioning, and 4) a larger reduction in symptom severity than working memory focused cognitive remediation administered with sham.

Specific Aim 2. The durability of intervention-induced changes in working memory, related cognitive domains, functional capacity, community functioning, and symptom severity will be examined in patients 6 weeks after working memory focused cognitive remediation with tDCS or sham. **Hypothesis 2:** We hypothesize that training gains achieved through pairing tDCS with working memory focused cognitive remediation will be maintained over time so that the predicted post-intervention between group difference in performance is sustained at 6 weeks post-intervention.

Achieving the proposed objectives will yield important information about the efficacy and durability of a novel pairing of cognitively enhancing interventions. Findings will inform treatment development with other cognitively compromised patient populations.

BACKGROUND AND SIGNIFICANCE

Despite pharmacological intervention, serious mental illnesses are among the leading causes of disability (1). This section will review the link between cognition and psychosocial functioning, highlight current efforts to address illness related cognitive impairments, and describe the development of cognitively enhancing interventions.

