Transfer of Working Memory Gains to Functional Outcomes. Development of cognitively enhancing interventions is motivated by the goal of reducing disability in schizophrenia. Recently, the results of two studies suggest that targeting working memory can have a measurable impact on functional outcomes (7, 60). Rispaud et al. (7) found that intervention-induced change in working memory and processing speed during a year of cognitive remediation was predictive of change in functioning, while changes in episodic memory and problem solving were unrelated to functional gains. Similarly, Subramaniam et al. (60) found that intervention induced change in working memory was predictive of vocational functioning at a six month follow up. Research suggests that transfer of cognitive gains to functional outcomes is facilitated by strategy training and opportunities to use cognitive skills with everyday activities (61). The addition of strategy training has been found to increase the impact of cognitive training on functional outcomes, $d=.47$ vs $.34$ (10), while action-based techniques that enable practice of cognitive skills in simulated environments has been found to produce significantly greater functional gains than cognitive training alone (62). Presently, the extent to which tDCS-induced cognitive gains can transfer to functional outcomes is unknown.

RESEARCH DESIGN AND METHODS

Participants will be randomized to a double-blind, double-baseline, sham controlled trial of a 48-session working memory focused cognitive remediation intervention paired with tDCS or sham. All participants who complete the 48-session intervention will be asked to return for follow up assessment 6 weeks post-intervention. A double-baseline design is being used to minimize measurement error, as the largest practice effects are observed between the first and second assessment. Given that very little is known about the durability of tDCS-induced change in cognition, the follow-up assessment will allow us to examine stability.

Participation in this study will be in addition to the clinical care that patients are receiving at study entry and will not replace psychiatric or case management services.

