Randomization. Group assignment will utilize a randomized block strategy, which is the preferred method of group assignment for small clinical trials of this nature (83). Accordingly, groups of 2 to 4 volunteers will be stratified into two groups so that patients assigned to each condition are equivalent in baseline N-back scores and age. We predict groups of this size will accumulate over 6-8 weeks of active recruitment. These stratified groups then will be assigned randomly to treatment conditions. The advantages of the randomized block strategy are that it maintains approximately equivalent group sizes throughout the trial, minimizes the confounding effects of initial differences (thereby decreasing reliance on statistical corrections such as ANCOVA), while at the same time preserving the interpretive strengths of unrestricted randomization.

Table 2. Training Session Protocol	
Training Activity	Time (min)
TDCS/Sham Set Up	5
Lesson Planning	5
Cognitive Training	60
TDCS/Sham Equipment Removal	5
Bridging Activities	45
Total	120

Intervention. The working memory focused cognitive remediation intervention will consist of two components: focused cognitive training and bridging activities. Participants will attend 2-3 120-minute training sessions a week. A typical session protocol is presented in Table 2. To be considered a completer, a participant must complete 80% (39 sessions) of treatment. To maximize treatment completion, make-up times will be available each week. In addition, participants will receive payments for completion of treatment sessions. The payment scale increases by \$1 after every 3 training sessions and ranges from \$10 dollars per a session for the first 3 training sessions and \$25 per a session for the last 3 training sessions.

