Study Blinds. To maximize the interpretability of any group differences that occur between the tDCS and sham conditions, multiple blinds will be in place. To equalize expectancy effects, patients will be blind to condition assignment. The StarStim neuromodulator will be used with all participants and is capable of offering a sham stimulation experience that is indistinguishable from tDCS. In addition, to minimize demand characteristics and differential provision of treatment, the interventionists who provide cognitive remediation will be blind to participant condition (tDCS vs sham). Furthermore, steps will be taken to blind the psychology technician who conducts the outcome assessments. Participants will be asked not to describe the intervention they are receiving to the psychology technician. In addition, the technician who conducts the outcome assessments will not provide the clinical intervention. The data collected will be coded in such a way that the investigator who conducts the data analysis will be blind to group membership.

Statistical Analysis Plan. T-tests will be conducted to determine whether important baseline variables are matched, such as working memory performance (N-back performance) and age. If any between-group differences emerge on these factors and they are found to relate to the dependent variables in any of the planned comparisons described below, the confounding variable will be added as a covariate of non-interest in the analysis.

Data Reduction: Consistent with recommendations that change in cognitive function be assessed with multiple measures of the construct (19), each working memory component will be assessed with two measures. Composite scores will be created by averaging the two measures of each aspect of working memory. Composite novel N-Back and novel complex span variables will represent performance on procedurally similar working

memory tasks with novel stimuli, composite scores on capacity, interference control, and goal maintenance tasks will reflect near transfer on untrained working memory measures, the MCCB Speed of Processing and Problem Solving and Reasoning composite will reflect far transfer to a related cognitive domain. Transfer to functional capacity and community functioning will be measured with performance on the UPSA-B Total score and the FE-SFS Total score. Impact on symptom severity will be assessed with the BPRS Total score and the BNSS Total score.

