Data Analysis Plan for Aims 1 and 2: Cognitive and functional improvements are considered equally important outcomes for interventions targeting cognition (64). The primary measures of cognitive outcome for this study will be the capacity, interference control, and goal maintenance composites. These variables were selected as the primary outcomes, as near transfer must be demonstrated for an intervention to be deemed cognitively enhancing (19). The measure of functional capacity, the UPSA-B Total score, will be the primary functional outcome. This is consistent with the NIMH criterion that improvement on a measure of functional capacity must be demonstrated in addition to cognitive improvement for an intervention to be classified as cognitively enhancing (86). Thus, near transfer and change in functional capacity are the outcomes that have been deemed to be clinically meaningful. Mixed model approaches will be used, as they are well-suited to examining within subject change over time.

Specific Aim 1: Near and Far Transfer of Training. Mixed effect, repeated measure ANOVAs will be completed to test the hypotheses that WMT and tDCS will enhance performance significantly more than WMT and sham on 1) novel versions of trained tasks, 2) untrained working memory measures, 3) measure of related cognitive functions, 4) functional capacity, and 5) community functioning. Symptom severity is predicted to improve significantly more with WMT and tDCS than WMT and sham. Significant Group x Time interactions will allow rejection of the null hypothesis that WMT + tDCS offers no benefit as compared to sham.

Specific Aim 2: Durability of Cognitive and Functional Changes. To examine durability of near and far transfer and symptom change, mixed model repeated measure ANOVAs will be conducted. TDCS-induced cognitive change is expected to endure and post-intervention between group differences maintained.

References

2. Gold JM. Cognitive deficits as treatment targets in schizophrenia. *Schizophr Res*. 2004;72(1):21-8.

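### Each outcome's own baseline should be a planned covariate, and each aim needs a named 1-df arm contrast: the planned interaction test is valid but leaves precision unused and gives Hypothesis 2 no estimate

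*Combined protocol and SAP*

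**What the plan says.** **Aim 1.** Data Analysis Plan for Aims 1 and 2 specifies mixed-effect repeated-measures ANOVAs and this decision rule: "Significant Group x Time interactions will allow rejection of the null hypothesis that WMT + tDCS offers no benefit as compared to sham". It does not list the levels of Time, the contrast or its degrees of freedom.

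**Aim 2.** The corresponding paragraph names only a type of model: "To examine durability of near and far transfer and symptom change, mixed model repeated measure ANOVAs will be conducted". Hypothesis 2 in Specific Aims is more definite. It predicts that "the predicted post-intervention between group difference in performance is sustained at 6 weeks post-intervention".

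**Baseline covariates.** Statistical Analysis Plan applies t-tests to important baseline variables, with N-back performance and age as its examples. Adjustment follows only on two conditions: "If any between-group differences emerge on these factors and they are found to relate to the dependent variables". Under Randomization, groups of 2 to 4 volunteers are split "so that patients assigned to each condition are equivalent in baseline N-back scores and age", and this is presented as reducing the need for ANCOVA.

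**Visits.** Table 1 schedules every cognitive, functional and symptom measure at two baselines, post-intervention and 6-week follow-up. The text introducing those measures names only three time points. Research Design and Methods gives the reason for the second baseline: "A double-baseline design is being used to minimize measurement error, as the largest practice effects are observed between the first and second assessment". How the two baselines enter the model is not stated. On follow-up the same section says: "All participants who complete the 48-session intervention will be asked to return for follow up assessment 6 weeks post-intervention".

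**The concern.** In a repeated-measures ANOVA with free arm means at every visit, baseline scores are responses. A baseline-to-post interaction then has the precision of a change score. Using the baseline as a covariate does at least as well in all but very small samples. The plan gives no outcome's own baseline a covariate role that applies regardless of imbalance. The conditional rule is unlikely to supply one, because its two named variables are those balanced by design. Balance on N-back and age also does not remove the outcome variance that the outcome's own baseline explains.

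The unlisted Time levels matter separately. With two baselines as separate levels, one degree of freedom compares two pre-treatment visits. If follow-up is also a level, a significant interaction could reflect a difference at 6 weeks alone. That would be a benefit, but not the post-intervention one. For Aim 2, the reader cannot tell which estimate answers Hypothesis 2.

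At stake are precision in a trial that Randomization itself describes as small, drawn from baseline assessments of about 5 hours each that are collected anyway, and a clear estimate for each aim.

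**Working it through.** The documents give no sample size, alpha, effect size or baseline-to-post correlation for this trial, so there is no planned figure to reproduce. What follows compares analyses under stated assumptions.

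**Inputs**
- From the measure descriptions: retest ICC .68-.85 for MCCB subtests, r = .93 over 2 weeks for the full UPSA, ICC .71-.90 for complex span. No retest coefficient is given for the capacity or goal-maintenance composites.
- Assumed: SD 1 at each visit, two-sided 5%, 40 per arm, effect 0.4 SD. Let *r* be the baseline-post correlation and *b* the correlation between baselines.

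**Variance per arm, in SD²**
- Change from second baseline: 2(1 − r)
- Change from mean baseline: 1 + (1 + b)/2 − 2r
- Adjusted for second baseline: 1 − r²
- Adjusted for mean baseline: 1 − 2r²/(1 + b)

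| r, b | Change, 2nd | Change, mean | Adjusted, 2nd | Adjusted, mean |
|---|---|---|---|---|
| 0.68, 0.68 | 0.640 | 0.480 | 0.538 | 0.450 |
| 0.70, 0.70 | 0.600 | 0.450 | 0.510 | 0.4235 |
| 0.93, 0.93 | 0.140 | 0.105 | 0.135 | 0.104 |
| 0.50, 0.80 | 1.000 | 0.900 | 0.750 | 0.722 |

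**Savings, equal correlations 0.68 to 0.93**
- Adjusted for mean v change from mean: 6% to 1%.
- Adjusted for second v change from second: 16% to 3.5%.
- Adjusted for mean v change from second: 30% to 26%. Of this, 25 points come from using both baselines, since 1.5(1 − r) is 75% of 2(1 − r).

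The quoted retest values cover 2 to 4 weeks or no stated interval, so 4-month correlations may be lower. At r = 0.5, b = 0.8 the three savings are 20%, 25% and 28%. In the other direction, simulation at 15 and 20 per arm with correlations of 0.85 gave a variance ratio of about 1.01 and 1.00 for adjusted v change from the mean baseline: no gain.

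**Power at post-intervention (r = b = 0.7)**

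For 1-df contrasts the noncentrality is 0.4/√(2V/40). For interactions it is (40/2) × SS/(1 − r), where SS is the sum of squares of the visit effects about their mean.
- Change from second baseline: V = 0.600, noncentrality 2.31, power 62.6%.
- 2-df interaction (two baselines, post): SS = 0.16 × 2/3, noncentrality 7.11, power 65.4%.
- Adjusted for second baseline: noncentrality 2.51, power 69.6%.
- Change from mean baseline: noncentrality 2.67, power 75.0%.
- Adjusted for mean baseline: noncentrality 2.75, power 77.5% (76.5% in simulation, which includes the cost of estimating the slope).
- 4-visit interaction, effect fully sustained: SS = 0.16, noncentrality 10.67, power 78.3%.
- 4-visit interaction, difference at 6 weeks only: SS = 0.16 × 3/4, noncentrality 8.0, rejects 64.6% of the time.

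**How often the covariate rule would act.** Taking the t-tests at 5%, simulations in which N-back and age are balanced within groups found an imbalance on either in about 0.2% to 5% of trials, depending on the splitting method and group sizes. Without effective balancing, as when all groups have 2 members, the figure is about 9%. The documents do not give the splitting rule, so none of these rates is a property of the plan. They support only the word seldom.

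**Why non-significance cannot show maintenance.** The 95% CI half-width for the post-to-6-week change in the arm difference is about 1.96 × √(2 × 0.600/40) = 0.34 SD, against an assumed effect of 0.4 SD. A non-significant change is compatible with losing most of the effect.

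**The case against.** Group x Time in a mixed model is a conventional and valid test, and own-baseline adjustment is an efficiency choice. That stands. A reader might infer that the planned test is biased or invalid; nothing in the documents supports this.

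A reader might also credit the whole 26-30% saving to the conditional covariate rule. That is wrong: most of it comes from using both baselines, which a change from the mean baseline would already do. If that is what the plan intends, adjustment adds 1-6% at equal correlations and 2.5 power points in the worked case (75.0% to 77.5%). But the plan does not state that contrast.

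A third tempting reading is that the Aim 1 test fails to isolate a post-intervention benefit. Durability is a separate aim, so the natural reading is that Aim 1's Time ends at post-intervention. The rule then isolates the right effect and only precision is lost. The objection to isolation applies only if follow-up is a level.

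The stated purpose of the double baseline suggests that the first visit may be there to absorb practice. That also stands: the second baseline alone is then the natural covariate, and the saving is 3.5-16%. The 3.5% end corresponds to the only coefficient given for the UPSA, which is for the full version.

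Finally, a model with baseline as a response keeps participants who lack one baseline, whereas a mean-baseline covariate is undefined for them. The fix therefore needs a rule for this.

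**Conclusion.** The point holds as one of precision and specification. The plan gives no outcome's own baseline an unconditional covariate role, does not list the levels of Time, and assigns no contrast to Hypothesis 2. An analysis at least as good in most settings is available from data already scheduled.

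The gain is modest to moderate and depends on what the plan intends. It is 1-6% of variance against change from the mean baseline, 3.5-16% with the second baseline alone, and 26-30% in total against change from the second baseline, all at assumed equal correlations of 0.68-0.93. It rises to 20-28% if the baseline-post correlation is 0.5 with 0.8 between baselines. It is negligible against change from the mean baseline at 15-20 per arm with correlations near 0.85. There is no power gain over a 4-visit omnibus test if the effect is fully sustained (77.5% v 78.3%). Sample size, effect size, alpha and 4-month correlations are all assumptions.

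A reader might take the 6-week contrast in the proposed model to describe only those who return. It does not. Participants with a post-intervention score but no 6-week score stay in the joint model and inform that contrast under missing-at-random. In a check where non-return depended on arm and post-intervention score, with a true difference of 0.40 SD, a returners-only analysis gave 0.51 and the joint model 0.40.

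**What to change.** For each outcome, prespecify one likelihood-based mixed model:
- **Responses:** post-intervention and 6-week scores, with unstructured covariance.
- **Terms:** arm, visit, arm x visit, the outcome's own baseline, and baseline x visit, whatever any imbalance test shows.
- **Baseline:** the mean of the two baselines, or the second alone if the first is meant only to absorb practice; say which. Use the available baseline when one is missing. A single covariate is safer than two separate ones in a small sample.
- **Aim 1:** the 1-df arm difference at post-intervention.
- **Aim 2:** the 1-df arm difference at 6 weeks with its 95% CI. Report the post-to-6-week change in the arm difference as an estimate with its 95% CI. Do not infer maintenance from a non-significant interaction.
- **Missing follow-up:** state that participants with a post-intervention score but no 6-week score remain in the model, that the 6-week contrast relies on missing-at-random for them, and that follow-up invitations go only to those who complete the intervention.

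The cost is SAP wording, about one degree of freedom per visit, and the rule for missing baselines. No extra participants, visits or measures are needed.

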Restoration of Cognitive Function with TDCS and Training in Serious Mental Illness

9/19/2022

NCT03208036

SPECIFIC AIMS

Development of interventions that can effectively target and remediate the cognitive and functional impairment associated with serious mental illness has been aggressively pursued and is a treatment priority. Transcranial direct current stimulation (tDCS) is a safe, non-invasive neuromodulation technique that is capable of stimulating brain activity to facilitate learning. As such, it shows promise as an adjunctive technique that could potentiate the impact of cognitive remediation and enhance cognition and functioning in this patient population.

The primary objective of this study is to evaluate the pairing of two therapeutic techniques, cognitive remediation and tDCS, as a cognitively enhancing intervention. The efficacy of a cognitively enhancing intervention is critically dependent on its capacity to improve performance on untrained tasks assessing the same cognitive domain. In addition, it would be highly desirable if intervention-induced change also generalized a) to improve functioning on cognitive domains beyond those that are trained and b) to improve capacity to perform real-world cognitive demands. To address this objective, this study is designed to address the following questions. Is cognitive remediation paired with tDCS more efficacious than cognitive remediation delivered with sham stimulation? Is intervention-induced cognitive change sustainable?

Specific Aims.

Specific Aim 1: To examine the incremental benefit of pairing tDCS with cognitive remediation, we will enroll outpatients with schizophrenia, schizoaffective disorder, or bipolar I disorder to a double-blind, double-baseline, sham-controlled study. Working memory focused cognitive remediation concurrent with tDCS or sham will be administered for 48 sessions. We will examine efficacy of the intervention with change on:

- a) novel versions of two working memory training tasks;
- b) untrained measures that assess three domains of working memory performance – goal maintenance, capacity, and interference control (near generalization);
- c) related cognitive constructs (far generalization);
- d) functioning, measured in terms of capacity as well as community participation; and
- e) symptom severity, measure in terms of overall symptom severity and severity of negative symptoms.

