Thus, development of new interventions that specifically address cognition has been ambitiously pursued. The mode of intervention that has shown the most potential is cognitive remediation, an intensive, behavioral intervention that engages cognitive processes through a highly structured learning experience. Restorative approaches to cognitive remediation aim to capitalize on neural plasticity, the brain's ability to alter its structure, function, and connectivity in response to environmental demands (8). Treatment protocols are structured to provide repeated practice with tasks that target and exercise a cognitive function. Two meta-analyses concluded that intensive cognitive training (24-50 sessions) was capable of modifying cognition in patients with schizophrenia (9, 10). Few studies have examined the impact of cognitive training in individuals with bipolar disorder, however a recent, well-powered clinical trial found improvement in multiple cognitive domains (121). However, effect sizes in the meta-analyses for intervention-induced cognitive change were modest ($d = .41-.45$), and these estimates have become controversial. Methodological weaknesses common in the field might have contributed to an overestimate of treatment effects (11, 12). Among recent, methodologically strong, studies, several have reported medium to large performance gains on training tasks but have failed to find evidence of transfer to untrained tasks (11, 13-16), although there have been some successes (17, 18). At present, the inconsistency with which generalization occurs significantly limits the viability of cognitive remediation as an intervention for this population.

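### The plan sets a joint standard of near transfer plus UPSA-B improvement, but its only decision sentence is not limited to those primary outcomes and never tests that standard

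*Combined protocol and SAP*

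**What the plan says.** The Specific Aims state the primary objective as evaluating the paired treatment "as a cognitively enhancing intervention". They make efficacy depend on untrained tasks in the same cognitive domain. On wider cognition and real-world demands they say only that "it would be highly desirable if intervention-induced change also generalized".

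The Data Analysis Plan for Aims 1 and 2 then sets the primary outcomes:

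- "The primary measures of cognitive outcome for this study will be the capacity, interference control, and goal maintenance composites", because "near transfer must be demonstrated for an intervention to be deemed cognitively enhancing".
- "The measure of functional capacity, the UPSA-B Total score, will be the primary functional outcome". The plan calls this choice consistent with a standard it attributes to NIMH: "improvement on a measure of functional capacity must be demonstrated in addition to cognitive improvement for an intervention to be classified as cognitively enhancing".

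The paragraph adds that near transfer and functional capacity are the outcomes regarded as clinically meaningful.

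The next paragraph (Specific Aim 1: Near and Far Transfer of Training) lists five outcome sets for mixed-model ANOVA: novel versions of trained tasks, untrained working memory, related cognition, functional capacity and community functioning. It adds a prediction for symptoms and ends with the only decision rule: "Significant Group x Time interactions will allow rejection of the null hypothesis that WMT + tDCS offers no benefit as compared to sham".

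No alpha level, testing order or multiplicity rule is given anywhere in the document.

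**The concern.** The primary hierarchy and the cited criterion sit in one paragraph and the decision sentence in the next, and nothing connects them. The decision sentence refers to one null hypothesis and to an unspecified set of interactions. It does not confine itself to primary outcomes, require both domains, or say how many interactions are needed. An interaction test also carries no direction of its own.

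As worded, the plan therefore does not prevent a gain on the novel N-back alone, or near transfer with no UPSA-B gain, from being reported as rejecting no benefit. The first case matters because N-back and complex span are trained in every session and are always the tasks performed during stimulation (Integration of Cognitive Training and TDCS). Of the recent trials with sound methods, the Background reports that "several have reported medium to large performance gains on training tasks but have failed to find evidence of transfer to untrained tasks". It treats inconsistent generalization as a serious limit on cognitive remediation. The present rule would allow the same pattern to be presented as efficacy.

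**Working it through.** The documents give no sample size, power or alpha, so there is no planned figure to reproduce. The finding rests on the text; the arithmetic shows its size.

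**Inputs from the document.** The outcome variables under Data Reduction are:

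- novel N-back and novel complex span (2)
- capacity, interference control and goal maintenance (3)
- the MCCB composite (1)
- UPSA-B and FE-SFS (2)
- BPRS and BNSS (2)

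The total is 2 + 3 + 1 + 2 + 2 = 10. The Complex Span task section says the novel complex span tasks also measure interference control. If those two composites are the same variable, the count is 9.

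**Assumptions.** Each test is two-sided at 0.05 and unadjusted. One significant interaction is enough. Correlation between test statistics is equal for all pairs and ranges from 0 to 0.9.

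**Step 1: independent outcomes, nothing works.** The chance of at least one false rejection is 1 − 0.95^k.

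- k = 10: 1 − 0.95^10 = 40.1%
- k = 9: 1 − 0.95^9 = 37.0%
- k = 4 (primary outcomes only): 1 − 0.95^4 = 18.5%

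**Step 2: correlated outcomes, nothing works.** Simulation of equicorrelated normal test statistics, 1,000,000 draws per correlation. The last column is the joint rule: UPSA-B significant and at least one of the three near-transfer composites significant, in either direction.

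| Correlation | Any of 10, either direction | Any of 10, favouring tDCS | UPSA-B and any of 3 |
|---|---|---|---|
| 0 | 40.1% | 22.4% | 0.7% |
| 0.3 | 35.2% | 17.8% | 1.2% |
| 0.5 | 28.8% | 14.4% | 2.0% |
| 0.7 | 21.3% | 10.7% | 2.9% |
| 0.9 | 12.8% | 6.4% | 4.0% |

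At correlation 0 the joint figure can be checked by hand: 0.05 × (1 − 0.95^3) = 0.05 × 0.1426 = 0.7%.

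**Step 3: the joint rule still needs a definition of near transfer.** Suppose UPSA-B truly improves and is certain to be detected, while near transfer does not occur. The joint claim is then false as often as the near-transfer part is.

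- Any of three, unadjusted: 1 − 0.95^3 = 14.3% if independent; 12.6% at correlation 0.5; 10.9% at 0.7.
- Any of three at 0.05/3: 1 − (1 − 0.05/3)^3 = 4.9% if independent; 4.5% at 0.5; 3.9% at 0.7. Holm's first step uses the same threshold, so with all three nulls true the chance of any false rejection is the same.
- All three required, each at 0.05: at most 5%, because any composite with no effect must itself be falsely significant.

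**The case against.** The strongest reply is that the two statements concern different claims. The requirement is about being classified as cognitively enhancing; the decision sentence is about offering no benefit. A plan may test benefit outcome by outcome and keep the stronger label for a stricter standard. That stands: a reader might infer a strict contradiction, and the text does not support one.

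A reader might also infer that the plan says any single outcome suffices. It does not. The sentence uses a plural, the hypotheses before it are numbered, and judging each by its own interaction is an ordinary reading. That reading still leaves unsaid how several results bear on the one null the sentence names.

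Nor can it be said that UPSA-B is left out of the decision. Functional capacity is the fourth item in the tested list; it is simply not made a necessary condition.

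Further, the NIMH criterion is cited to support the choice of endpoint, not written as this trial's success rule. The Specific Aims call real-world generalization only desirable and place all outcome groups under efficacy. This stands too, and it means the plan's own sections must be reconciled before a joint rule can be called its settled standard.

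Finally, if the trained-task versions truly improve more with tDCS, rejecting no benefit on them is a correct result. The gap should therefore not be measured by setting power on a trained task against the false-positive risk of the joint claim. The Background also mentions some successes in transfer, and the novel variants are meant to assess transfer to similar tasks with new content.

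None of this supplies the missing link. Primary outcomes are named, but no sentence says the conclusion depends on them.

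**Conclusion.** The concern holds as a failure to carry the plan's primary hierarchy and cited criterion into its decision rule. The document names four primary variables in two domains, makes cognitive enhancement its objective, and cites a standard requiring both domains. It then gives a single rule that neither restricts itself to those variables nor requires both domains.

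If any one of ten significant results may reject the null, the chance of at least one false rejection when nothing works is about 40% with independent outcomes and about 29% at correlation 0.5. Counting only results that favour tDCS, it is about 22% and 14%. These figures depend on the assumed any-one reading, the assumed unadjusted two-sided 0.05 and the assumed correlations. The textual finding does not.

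The primary set has a related weakness. Interference control is measured with novel versions of the trained complex span tasks, so a near-transfer result could rest on a trained paradigm. The point should be addressed before group codes are broken.

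**What to change.** 1. **Efficacy conclusion.** Base it on the primary outcomes only, with effects favouring tDCS at the post-intervention visit. State that the novel trained-task versions, far transfer, FE-SFS, BPRS and BNSS are secondary and cannot by themselves reject the no-benefit null.
2. **The label.** Reserve the conclusion that the pairing is cognitively enhancing for near transfer and UPSA-B together. Report near transfer without UPSA-B as cognitive transfer only. Reconcile the Specific Aims, where functional generalization is desirable, with the Data Analysis Plan, where it must be shown.
3. **Near transfer.** Define it, for example as at least one of the three composites after Holm adjustment across the three, or all three at 0.05. Interference control should not establish it alone, given its overlap with the trained complex span tasks.
4. **Alpha.** State the level. No alpha is split between near transfer and UPSA-B when both are required, but adjustment within the three composites is needed if fewer than all three suffice. If either domain alone were allowed to reject no benefit, alpha would have to be shared: two domains each at 0.05 give 1 − 0.95^2 = 9.8% if independent.

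The cost is a few SAP sentences and no new data. The drawback is that the full claim becomes harder to reach, and the documents give no sample size from which to say by how much.
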